5.1 Simulations with Sample Size Re-estimation

Simulations for the proposed GSD with SSR in Section 5 were carried out under the null hypothesis (sensitivity $\leq .8$ and/or specificity $\leq .5$) while varying the prevalence from 35% to 65%. Power from 10,000 monte-carlo runs for different combinations of sensitivity and specificity in Table 8-1 show that the type-I error is preserved at the 2.5%.

Simulations under the alternative (sensitivity > .8 and specificity > .5 for the primary and the first two secondary endpoints) show that for prevalence varying between 35% and 65%, sensitivity around 90% and specificity greater than 60% the power achieved is greater than 90% for a expected sample size between 950 and 1050 subjects under the adaptive group sequential design.

Prev.	Se	Sp	Prop. ChangeTH	Prop. Futility stop at IA1	Overall Power	Min.N	Avg.N	Max.N
0.35	0.80	0.50	0.05	0.93	0.0004	876	882	1300
0.50	0.80	0.50	0.05	0.94	0.0001	876	882	1300
0.65	0.80	0.50	0.07	0.92	0.0000	876	884	1300
0.35	0.85	0.50	0.19	0.77	0.0094	876	904	1300
0.50	0.85	0.50	0.18	0.78	0.0106	876	904	1300
0.65	0.85	0.50	0.21	0.75	0.0137	876	909	1300
0.35	0.90	0.49	0.40	0.57	0.0150	876	930	1300
0.50	0.90	0.49	0.39	0.58	0.0160	876	929	1300
0.65	0.90	0.49	0.40	0.57	0.0144	876	931	1300
0.35	0.80	0.55	0.16	0.78	0.0088	876	900	1300
0.50	0.80	0.55	0.16	0.80	0.0067	876	899	1300
0.65	0.80	0.55	0.19	0.77	0.0046	876	902	1300
0.35	0.79	0.60	0.33	0.63	0.0062	876	916	1300
0.50	0.79	0.60	0.35	0.61	0.0052	876	919	1300
0.65	0.79	0.60	0.35	0.62	0.0037	876	918	1300

Table 5-1: Simulation results under the Union Null Hypothesis for proposed group sequential design with thresholding at interim-1 and SSR at the last interim, for varying prevalence, sensitivity and specificity.

Prev.: Data generating prevalence

Se: Data generating Sensitivity

Sp: Data generating Specificity

Prop ChangeTH: Proportion of runs where threshold was changed at IA-1

Prop. Futility Stop at IA-1: Futility Futility stopping triggered at IA-1, however simulations carried out under non-binding futility

Overall Power: Power to detect at least the primary hypothesis

Min.N, Avg.N, Max.N: All calculated over 10,000 runs with non-binding futility

Prev.	Se	Sp	Prop. ChangeTH	Overall Power	Power to Reject All 3 endpoints	Min.N	Avg.N	Max.N
0.35	0.90	0.60	0.34	0.995	0.894	250	969	1300
0.45	0.90	0.60	0.33	0.993	0.903	250	946	1300
0.55	0.90	0.60	0.33	0.979	0.901	250	989	1300
0.65	0.90	0.60	0.36	0.947	0.829	250	1044	1300
0.35	0.85	0.65	0.74	0.625	0.258	525	1091	1300
0.45	0.85	0.65	0.65	0.741	0.406	525	1100	1300
0.55	0.85	0.65	0.57	0.829	0.538	525	1105	1300
0.65	0.85	0.65	0.48	0.881	0.614	525	1103	1300
0.35	0.92	0.55	0.56	0.705	0.342	525	1082	1300
0.45	0.92	0.55	0.62	0.647	0.275	525	1079	1300
0.55	0.92	0.55	0.64	0.580	0.192	525	1070	1300
0.65	0.92	0.55	0.63	0.481	0.098	876	1054	1300
0.35	0.92	0.58	0.41	0.969	0.828	525	1026	1300
0.45	0.92	0.58	0.46	0.941	0.803	250	1050	1300
0.55	0.92	0.58	0.50	0.908	0.734	525	1080	1300
0.65	0.92	0.58	0.54	0.836	0.580	525	1089	1300

Table 5-2: Simulation results under the Intersection Alternate Hypothesis for proposed group sequential design with thresholding at interim-1 and SSR at the last interim, for varying prevalence, sensitivity and specificity.

Prev.: Data generating prevalence

Se: Data generating Sensitivity

Sp: Data generating Specificity

Prop ChangeTH: Proportion of runs where threshold was changed at IA-1

Overall Power: Power to detect at least the primary hypothesis

Min.N, Avg.N, Max.N: All calculated over 10,000 $\,$

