3.1 Success Criteria and Hypothesis Testing

The success criteria for the DDS device validation trial is that the sensitivity is greater than 80% with a specificity greater than 50%. The sensitivity and the specificity will be estimated using an independent validation dataset. The following one-sided hypothesis testing will be carried out:

$$H_0 : H_0^{se} \cup H_0^{sp} \text{ vs.}$$

$$H_A : H_A^{se} \cap H_A^{sp},$$
(1)

where,

 $\begin{array}{lll} H_0^{se} & : & \mathrm{Sensitivity} \leq .8, \\ H_A^{se} & : & \mathrm{Sensitivity} > .8, \\ H_0^{sp} & : & \mathrm{Specificity} \leq .5, \text{ and} \\ H_A^{sp} & : & \mathrm{Specificity} > .5. \end{array}$

Each of H_0^{se} vs. H_A^{se} and H_0^{sp} vs. H_A^{sp} will be tested at one-sided 2.5% level of significance which will (conservatively) preserve the over-all type-I error for testing H_0 vs. H_A .

The same hypothesis test as in (1) will be applied to the secondary endpoints. Hypothesis will be carried out in a hierarchical fashion to ensure that the type-I error is controlled at the one-sided 2.5% level.

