3.2 Determination of Sample Size

The power and the sample size to test the hypothesis depends on several unknown parameters:

- 1. Subject level prevalence;
- 2. The prevalence of impaired swallows conditional on subject having Dysphagia;
- 3. The true sensitivity and specificity of the DDS device in detecting swallow impairment; and
- 4. The optimum threshold on the ROC curve.

Based on estimates from the exploratory study data, if the DDS is assumed to have a sensitivity and specificity of at least 86% and 60% respectively and approximately 35% patients show impaired safety, then a power of 90% to test H_0 vs. H_A (from equation (1)) can be achieved with 700 to 800 subjects under a fixed design. Considering that data from additional 100 to 200 subjects may be used for threshold calibration, the starting sample size is 900 subjects. A sample size re-estimation will be carried out at the last interim analysis. The maximum sample size is set to 1300 (see Table 5-2).

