3.3 Group Sequential Design (GSD)

The clinical trial will initially start as a 3-look GSD. Alpha-spending will be calculated using Lan-DeMets spending function with O'Brien-Fleming parameter (LDOF) [2]. At the first interim analysis (IA-1) the threshold on the ROC curve may be re-computed using the ROC curve generated using the IA-1 data, in which case, the validation trial would start afresh following IA-1 using a 2-look GSD. Data included in the IA-1 would no longer be used for the validation phase. If the threshold is not re-computed at the first interim and the efficacy boundary has not been crossed then the trial continues as planned as a 3-look GSD.

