3.4 Timing of Interim Analysis-1

The overall subject-level prevalence of impaired safety and efficiency as determined by the central lab VFS reading will be continuously monitored in a blinded fashion, i.e. the study staff will be blinded to the DDS results. The first interim analysis will be performed when the prevalence can be estimated using a 95% confidence interval of width no more than 15%. Thus if the true (subject-level) prevalence is 20% then the interim analysis may be carried out after 110 subjects. On the other hand if the prevalence is around 50% then around 170 subjects would be needed. If the monitoring is carried out after every 50 subjects have completed the study, the first interim will be carried out around completion by 200 subjects.

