3.11.1 Interim Analysis - 1 (IA-1)

The main objective of IA-1 is to determine if the fixed threshold (fixed using phase-0 data) applied to the ROC curve obtained using IA-1 data is still optimal or whether a new threshold obtained from the IA-1 data should be used moving forward. In case the threshold is changed then the validation trial re-starts while excluding the IA-1 data for testing validation related hypotheses.

The Analysis plan for IA-1 are listed as follows:

- 1. Compute AUC for the ROC curve based on IA-1 data
- 2. If AUC < .75, consider futility analysis. Note that this futility rule is non-binding.
- 3. Otherwise, calculate sensitivity, specificity both with the fixed threshold from phase-0 data as well as the optimal threshold on the IA-1 ROC curve.
- 4. The benefit versus the cost of changing the threshold will be analyzed. This will be done by comparing the conditional power at IA-1 under the old threshold and a total sample size of N = 900 ($CP_{old,900}$) with the power of a restarted trial using the new threshold and sensitivity-specificity estimates obtained at IA-1 using this new threshold along with the prevalence estimate obtained at IA-1. If the power of the restarted trial with $N = 900 - N_1$ is greater than $CP_{old,900}$ then the benefit of changing the threshold is clear. Here N₁ is the number of subjects included in the IA-1 analysis. If this is not the case then the power of the restarted trial with N = 900 ($P_{new,900}$) will be compared to $CP_{old,900}$. Since conditional power and power will be calculated for testing both sensitivity and specificity for the primary endpoint the formal guideline (established using simulations) is defined in terms of the product of the two as follows:

If $P_{new,900-N_1,SE} \times P_{new,900-N_1,SP} > CP_{old,900,SE} \times CP_{old,900,SP}$ then change threshold; OR

If $P_{new,900,SE} \times P_{new,900,SP} > CP_{old,900,SE} \times CP_{old,900,SP} + 0.025$ then change threshold.

The above statistical logic offers a guideline for changing the threshold, however clinical justification may overrule the statistical guideline in this matter.

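### Does Table 5-1 leave the 2.5% type-I error of the restart design in doubt?

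*SAP*

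**What the plan says.** SAP 3.1 requires both sensitivity above .80 and specificity above .50, each "tested at one-sided 2.5% level of significance which will (conservatively) preserve the over-all type-I error". SAP 3.3 and 3.10.2 add Lan-DeMets O'Brien-Fleming spending. If the threshold is revised at the first interim, the first-interim data are dropped, "in which case, the validation trial would start afresh following IA-1 using a 2-look GSD". SAP 3.11.1 makes that choice depend on first-interim results, through conditional power and projected power.

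SAP 5.1 states that the null simulations, 10,000 runs per point, "show that the type-I error is preserved at the 2.5" percent level. It cites Table 8-1, but the table that follows is 5-1. The (sensitivity, specificity) pairs in it are .80/.50, .85/.50, .90/.49, .80/.55 and .79/.60, each at prevalence .35, .50 and .65. The largest rejection rate is .0160. The legend reads "Overall Power: Power to detect at least the primary hypothesis" and, on futility, "Futility stopping triggered at IA-1, however simulations carried out under non-binding futility".

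**The concern.** When both measures must succeed, the chance of a false claim is roughly the error of the measure at its limit times the power of the other. It is largest with one measure exactly at its limit and the other comfortably above. Table 5-1 avoids those points: .90 is paired with .49, and .60 with .79, which puts both pairs inside the null. The pairs that do sit at a limit have weaker partners. The omitted values are realistic, since SAP 3.2 plans on the basis "if the DDS is assumed to have a sensitivity and specificity of at least 86% and 60% respectively" and Table 5-2 uses sensitivity .90 and specificity .60 and .65.

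The column also does not separate false rejections from correct ones at a revised threshold that truly meets both targets. Because the restart depends on interim results and carries a full 2.5%, a reader may ask whether a pivotal error-control claim rests on a table that could not have shown a failure.

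**Working it through.** **Inputs.** Test statistics and limits (.80, .50) from SAP 3.7; one-sided 2.5% from SAP 3.1; grid, rates and 10,000 runs from SAP 5.1; N = 876 from Min.N in Table 5-1. The simulated ROC model is not stated, so the table cannot be reproduced exactly. A plain fixed test is the yardstick.

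**Plain test.** For each measure, with true value p, limit p0 and n diseased or healthy subjects,

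power = Φ{[√n (p − p0)/√(p0(1 − p0)) − 1.96] / √[p(1 − p)/(p0(1 − p0))]},

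and the rejection rate is the product of the two. Example, .85/.50 at prevalence .35: n = 876 × .35 = 306.6; √306.6 × .05/.4 = 2.189; SD ratio √(.85 × .15)/.4 = .893; Φ((2.189 − 1.96)/.893) = .601; × .025 = .0150.

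| Se/Sp | Plain test, prevalence .35/.50/.65 | Table 5-1 |
|---|---|---|
| .80/.50 | .0006 each | .0004/.0001/.0000 |
| .85/.50 | .0150/.0192/.0219 | .0094/.0106/.0137 |
| .80/.55 | .0166/.0138/.0104 | .0088/.0067/.0046 |
| .79/.60 | .0093/.0073/.0057 | .0062/.0052/.0037 |
| .90/.49 | .0074/.0087/.0104 | .0150/.0160/.0144 |
| .86/.50 | .0195/.0228/.0242 | not listed |
| .90/.50 | .0250 each | not listed |
| .80/.60 | .0249/.0247/.0236 | not listed |
| .80/.65 | .0250 each | not listed |

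The omitted points are therefore the worst case, but a plain test there sits at 2.5% and not above it.

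**Could the listed rows have shown inflation?** Dividing each table rate by the partner's power gives the implied error at the limit.

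- .85/.50: .0094/.601 = .0156; .0106/.769 = .0138; .0137/.874 = .0157.
- .80/.55: .0088/.666 = .0132; .0067/.553 = .0121; .0046/.417 = .0110.

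The smallest shortfall from a 2.5% component error is (.0150 − .0094)/√(.0150 × .985/10,000) = .0056/.00122 = 4.6 Monte Carlo standard errors. These six rows could have shown inflation, and they show the opposite.

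**What the column counts.** False rejections cannot exceed all rejections. If the column holds all rejections, the false rate is lower than printed. If it holds false ones, it is the rate wanted. Either way it is at most .0160 at the listed points, provided runs flagged for futility are counted. Min.N is 876 in all 15 null rows although 57% to 94% of runs were flagged, so flagged runs did continue.

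**The restart.** With IA-1 at information fraction t, a free choice between continuing and restarting at full alpha has expected error at most E[max(A, .025)], where A = 1 − Φ((1.96 − √t·z)/√(1 − t)). This is .0360 at t = 200/900 and .0373 at t = 250/900, for one measure at its limit before and after the restart. Simulations at the omitted points gave:

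- Both measures unchanged after the restart, no futility gate: .030 to .038, with the threshold changed in 76% to 80% of runs.
- The same with a futility-type gate and flagged runs counted: .023 to .034.
- Binormal ROC setting the new values (diseased SD 1.0 or .65 relative to healthy; new threshold by Youden or by maximum power product; 40,000 runs): false rejections .004 to .021, maximum .0207 ± .0014.

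The unchanged-values model is hard to square with the table. At .90/.49 it changes the threshold in 84% to 85% of runs, against 39% to 40% tabulated.

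**Consistency of the simulation.** SAP 3.11.1 says "If AUC < .75, consider futility analysis. Note that this futility rule is non-binding". At .90/.49 the table shows 57% to 58% flagged. A binormal curve through that point triggers the rule in about 1% to 3% of runs with diseased SD 1.0, but in about 47% to 49% with SD .65 and 60% to 64% with SD .60 (200 to 250 subjects). Ordinary unequal-variance curves thus give the tabulated size. Min.N of 250 in Table 5-2 does not contradict "the first interim will be carried out around completion by 200 subjects".

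**The case for a change.** The strongest case is that the simulation is the only evidence offered for the data-dependent restart. Spending and the 2.5% component tests cover a fixed threshold. Dropping the first-interim data makes the restarted test valid on its own, but not the choice of when to restart, and a ceiling of .036 to .037 exists. At .90/.49, nearest the omitted .90/.50, the table exceeds a plain test by a factor of 1.4 to 2.0, which is 3 to 6 Monte Carlo standard errors. A rough gate model fits three of the five pairs better if flagged runs are left out of the count.

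This stands in part. The table does not establish the maximum, the model is not written out, and leaving flagged runs out of the count cannot be excluded, although the legend and Min.N point the other way. It stops short of showing inflation. A threshold change moves along an ROC curve, so specificity at its limit does not normally stay there: it rises, and the rejection may be correct, or sensitivity falls. At .90/.49 the excess may include correct rejections at a revised threshold, and the total is still below 2.5%. The ceiling needs one measure exactly at its limit both before and after the change.

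**Conclusion.** No change to the plan follows. The claim in SAP 5.1 is worded more strongly than its grid supports, and the Table 8-1 pointer is a clerical slip, but the gap lies in the reporting of supporting simulations. The worst case for a plain test is .025. Under the ROC models tried, the false-rejection rate at the omitted points peaked at .0207. Only the assumption that both measures stay put after a revision takes it clearly above 2.5%, to .038 at most. More null rows and a written-out model would help a reader, and the simulation team can supply them from its own code. They would leave alpha, sample size, boundaries and the restart rule as they are.

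Confidence is moderate. The conclusion rests on assumed binormal curves and threshold criteria that are not in the documents, on flagged runs being counted in Table 5-1, and on the restart guideline being followed. The clinical override allowed in SAP 3.11.1 cannot be simulated as written.

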5.2 Interim Analysis Plan Flowchart

The different interim analysis plans are summarized in Figure 5.1 below.

Figure 5-1: Flowchart for Interin Analysis Plans\$24\$
